	
 
Solicited local adverse events, including redness/erythema, swelling/induration, pain and limitation of arm movement within 30 minutes of vaccination and over the 3-day period post vaccination (Day 0-3).
 
Solicited systemic adverse events, including fever fatigue/malaise muscle VEC aches, joint aches, chills, nausea and headache within 30 minutes of vaccination and over the 3-day period post vaccination (Day 0-3).
 
Unsolicited adverse events (AEs) occurring within 30 days post vaccination ROPICAL MEDICIN
 

• Serious Adverse Events (SAE) occurring during the entire study period (Days 0-90).

Occurrences of all events will be reported and summarized according to event severity, as "any local AE", or "any systemic AE", and by relationship to administration of study product, as deemed by a blinded study clinician. Percentage of participants experiencing each reaction or event, or at least one reaction or event will be calculated along with two-sided exact 95% CIs. The percentage of participants with solicited AE and SAEs will be compared between vaccine and comparator groups and a two-sided p-value of 0.05 will be considered statistically significant.

Inferential analyses

GMT ratios (GMT active comparator vaccine/GMT GPO Tri Fluvac) and difference of seroconversion rate (with two-sided 95% CI) related to the comparisons of interest will be computed. Acceptance value of GMT ratios at  $\leq 1.5$  and/or difference of seroconversion rate at  $\leq 10\%$  for the upper bound of the 95% CI will be considered for non-inferiority.

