# **Primary Safety Endpoints:**

The number and proportion of participants reporting the following events will be assessed:

- Solicited local adverse events, including redness / erythema, swelling / induration, pain, and limitation of arm movement within 30 minutes of vaccination and over the 3-day period post-vaccination (Days 0-3).
- Solicited systemic adverse events, including fever, fatigue/malaise, muscle aches, joint aches, chills, nausea, and headache within 30 minutes of vaccination and over the 3-day period post-vaccination (Day 0-3).
- Unsolicited Adverse Events (AEs) occurring within 90 days post-vaccination.
- Serious Adverse Events (SAE) occurring during the entire study period (Days 0-90).

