## II. Definitions of terms used in the Table:

Basic Self-care Functions Adult

Activities such as bathing, dressing, toileting, transfer/movement, continence, and feeding.

LLN Lower limit of normal

Medical Intervention Use of pharmacologic or biologic agent(s) for treatment of an AE

NA Not Applicable

Operative Intervention Surgical OR other invasive mechanical procedures.

ULN Upper limit of normal

Usual Social & Functional Activities Adult

Adaptive tasks and desirable activities, such as going to work, shopping, cooking, use of transportation, pursuing a hobby, etc.

PARAMETER	GRADE 1 MILD	GRADE 2 MODERATE	GRADE 3 SEVERE	GRADE 4 POTENTIALLY	
ESTIMATING SEVERITY GRADE					
SYSTEMIC					
Acute Allergic Reaction	Localized urticaria (wheals) with no medical intervention indicated	Localized urticaria with intervention indicated OR Mild angioedema with no intervention indicated	Generalized Urticaria OR Angioedema with intervention indicated OR Symptoms of mild bronchospasm	Acute anaphylaxis OR Life- threatening bronchospasm OR Laryngeal edema	
Chills	Symptoms causing no or minimal interference with usual social & functional activities	Symptoms causing greater than minimal interference with usual social & functional activities	Symptoms causing inability to perform usual social & functional activities	NA	
Fatigue or Malaise Report only one	Symptoms causing no or minimal interference with usual social & functional activities	Symptoms causing greater than minimal interference with usual social & functional activities	Symptoms causing inability to perform usual social & functional activities	Incapacitating symptoms of fatigue or malaise causing inability to perform basic self- care functions	
Fever (non-axillary	38.0 to < 38.6°C	$\geq$ 38.6 to < 39.3°C	$\geq$ 39.3 to < 40.0°C	≥40.0°C	
Fever (axillary)	37.7 – 38.1°C	38.2 – 38.8°C	38.9 - 40.0°C	>40.0°C	
Nausea	Transient (< 24 hours) or intermittent AND No or minimal interference with oral intake	Persistent nausea resulting in decreased oral intake for 24 to 48 hours	Persistent nausea resulting in minimal oral intake for > 48 hours OR Rehydration indicated (e.g., IV fluids)	Life-threatening consequences (e.g., hypotensive shock)	

HICS COMMITTEE Page 67 Aut 7.9 OF TROPICAL MEDICINE าริตยาลัยม MAHIDOL UNIVERSITY

APPROVED

US

R

ES
PARAMETER	GRADE 1 MILD	GRADE 2 MODERATE	GRADE 3 SEVERE	GRADE 4 POTENTIALL Y LIFE- THREATENIN

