Vomiting	Transient or intermittent AND No or minimal interference with oral intake	Frequent episodes with no or mild dehydration	Persistent vomiting resulting in orthostatic hypotension OR Aggressive rehydration indicated (e.g., IV fluids)	Life-threatening consequences (e.g., hypotensive shock
Headache	Symptoms causing no or minimal interference with usual social & functional activities	Symptoms causing greater than minimal interference with usual social & functional activities	Symptoms causing inability to perform usual social & functional activities	Symptoms causing inability to perform basic self-care functions OR Hospitalization indicated OR Headache with significant impairment of alertness or other neurologic function
INJECTION SITE	REACTIONS			
Injection Site Pain or Tenderness Report only one	Pain or tenderness causing no or minimal limitation of use of limb	Pain or tenderness causing greater than minimal limitation of use of limb	Pain or tenderness causing inability to perform usual social & functional activities	Pain or tenderness causing inability to perform basic self- care function OR Hospitalization indicated
Injection Site Erythema or Redness Report only one > 15 years of age	2.5 to < 5 cm in diameter OR 6.25 to < 25 cm2 surface area AND Symptoms causing no or minimal interference with usual social & functional activities	$\geq$ 5 to < 10 cm in diameter OR $\geq$ 25 to < 100 cm2 surface area OR Symptoms causing greater than minimal interference with usual social & functional activities	$\geq$ 10 cm in diameter OR $\geq$ 100 cm2 surface area OR Ulceration OR Secondary infection OR Phlebitis OR Sterile abscess OR Drainage OR Symptoms causing inability to perform usual social & functional activities	Potentially life- threatening consequences (e.g., abscess, exfoliative dermatitis, necrosis involving dermis or deeper tissue)

Protocol: GPO Tri Fluvac Vaccine Phase II/III\_ Version 3.1 dated 13 Mar 2017

MUINE MAHIDOL UNIVERSITY

E.

PARAMETER GRADE 1 MILD		GRADE 2 MODERATE	GRADE 3 SEVERE	GRADE 4 POTENTIALLY LIFE-
Injection Site Induration or Swelling Report only one > 15 years of age	Same as forSame as forInjection SiteImageErythema orImageRedness, $> 15$ ImageyearsImage	Same as for Injection Site Erythema or Redness, > 15 years of age	Same as for Injection Site Erythema or Redness, > 15 years of Age	Same as for Injection Site Erythema or Redness, > 15 years of age

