	Tri fluvac (N = xx)	Comparator (N = xx)	Tri fluvac (N = xx)	Comparator (N = xx)	Tri fluvac (N = xx)	Comparator (N = xx)	Tri fluvac (N = xx)	Comparator (N = xx)
Min, Max								
P- value =								

	D	Day 0 Day 7		Day 21		Day 90		
	Tri fluvac (N = xx)	Comparator (N = xx)	Tri fluvac (N = xx)	Comparator (N = xx)	Tri fluvac (N = xx)	Comparator (N = xx)	Tri fluvac (N = xx)	Comparator (N = xx)
HEENT, n (%)								
Normal	xx(xx.xx)	xx(xx.xx)						
Abnormal	xx(xx.xx)	xx(xx.xx)						
P- value =	X.2	xxxx						
Lungs, n (%)								
Normal								
Abnormal								
P- value =								
Cardiovascular, n (%)								
Normal								
Abnormal								
P- value =								
Gastrointestinal, n (%)								
Normal								
Abnormal								
P- value =								
Musculoskeletal, n (%)								
Normal								
Abnormal								
P- value =								
Skin, n (%)								
Normal								
Abnormal								
P- value =								

TREF 3.4: Physical Examination by GPO Tri Fluvac and Active Comparator Group

	Day 0		D	Day 7		Day 21		Day 90	
	Tri Fluvac (N = xx)	Comparator (N = xx)	Tri Fluvac (N = xx)	Comparator (N = xx)	Tri Fluvac (N = xx)	Comparator (N = xx)	Tri Fluvac (N = xx)	Comparator (N = xx)	
Neurologic, n (%)	X	((
Normal	xx(xx.xx)	xx(xx.xx)							
Abnormal	xx(xx.xx)	xx(xx.xx)							
P- value =	X XXXX								

TREF 3.4: Physical Examination by GPO Tri Fluvac and Active Comparator Group (Continue)

TREF 3.5: Comparison of Maximum Grade of Any Local Reaction at Post Immunization by GPC
Tri fluvac and Active Comparator Group

Grade		Tri Fluvac (N = xx) n (%)	Comparator (N = xx) n (96)
Grada 0			
Grade 0		XX(XX.XX)	XX(XX.XX)
Grade 1		XX(XX.XX)	XX(XX.XX)
Grade 2		xx(xx.xx)	xx(xx.xx)
Grade 3		xx(xx.xx)	xx(xx.xx)
P- value =	X.XXXX		

Note: - Any local reaction on any day (by case)

- Erythema and Induration will be not included.

- Grading

- Grade 0 none
- Grade 1 mild
- Grade 2 moderate
- Grade 3 severe

TREF 3.6: Comparison of Local Reaction at Post Immunization each Follow up Time by GPO Tri Fluvac and Active Comparator Group

	30	min	D	Day 1	D	ay 2	Da	ny 3
Local Reaction	Tri Fluvac	Comparator						
	(N=xx)							
- Pain, n (%)	xx(xx.x)	xx(xx.xx)						
p-value =	X.:	xxxx						
- Limitation of arm movement, n (%)								
p-value =								
- Erythema (cm.)								
n								
Mean(SD)								
Median								
Min, Max								
p-value =								
- Swelling (cm.)								
n								
Mean(SD)								
Median								
Min, Max								
p-value =								
- Induration (cm.)								
n								
Mean(SD)								

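### Fatigue/malaise is one reaction in the primary safety endpoint, but the SAP tabulates and tests it as two; swelling/induration gets no percentage or grade at all

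*Protocol*

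**What the plan says.** **Endpoint.** Section 3 of the protocol lists "Solicited systemic adverse events, including fever, fatigue/malaise, muscle aches, joint aches, chills, nausea, and headache". The Protocol Summary ("Solicited systemic adverse events, including fever fatigue/malaise muscle"), sections 8.2 and 11.3.2, and the SAP's own Study Synopsis also join fatigue and malaise with a slash. The local list in the Protocol Summary reads "Solicited local adverse events, including redness/erythema, swelling/induration, pain and limitation of arm movement", so swelling/induration is likewise one item.

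**Statistic.** The Protocol Summary asks for a rate for each reaction: "Percentage of participants experiencing each reaction or event, or at least one reaction or event will be calculated", with two-sided exact 95% CIs. It also plans a between-arm comparison of solicited events.

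**Grading.** Appendix A has one line for each pair: "Fatigue or Malaise Report only one" and "Injection Site Induration or Swelling Report only one".

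**Systemic shells.** TREF 3.11 gives fatigue and malaise separate n (%) rows and p-values by time point. TREF 3.12 grades them separately, TREF 3.13 counts their days separately, and TREF 3.14 runs from no symptom to nine.

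**Local shells.** TREF 3.6 has one size row for swelling and another for induration ("Induration (cm"), each with n, mean, median, range and a p-value, among cases who had the symptom. TREF 3.7, 3.8 and 3.9 cover only pain and limitation of arm movement. The notes to TREF 3.5 and FREF 07 leave out erythema and induration and do not mention swelling.

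**Contrary wording.** Protocol section 11.4 separates fatigue and malaise with a comma, while keeping swelling and induration joined by a slash.

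**The concern.** A reaction named in the primary safety endpoint should have a table row that reports it. Fatigue/malaise has none; it has two rows, each holding part of it. If sites follow Appendix A and record one label per complaint, each row understates the reaction. If participants can mark both labels, one complaint counts as two symptoms in TREF 3.14. Either way, the required percentage with its exact CI is not a planned output, and the planned p-values test something other than the defined reaction.

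Swelling/induration has a different gap. The plan describes how large the swelling or induration was among those who had it, but not how many participants had the reaction or at what grade. At stake are the per-reaction rates of the primary safety endpoint.

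**Working it through.** The check compares texts, counts rows, and bounds the combined rate.

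**1. Reproduce the SAP's maximum of nine.** The rows of TREF 3.11 to 3.13 are headache, fatigue, malaise, chills, myalgia, arthralgia, nausea, vomiting and rash: nine. This matches TREF 3.14 only if fatigue and malaise are two symptoms. As one reaction, the maximum is 9 − 1 = 8.

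**2. Local rows.** TREF 3.6 lists pain, limitation of arm movement, erythema, swelling and induration: five rows, or four with swelling/induration as one reaction. TREF 3.9 stops at two symptoms, which are pain and limitation of arm movement.

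**3. What each shell yields for the defined reaction.**

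| Reaction | n (%) | Grade | Exact 95% CI | Between-arm test |
|---|---|---|---|---|
| Fatigue/malaise | two part-rows, none combined | two part-rows, none combined | none in the shells | one per part |
| Swelling/induration | none | none | none | on size among cases, one per part |

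**4. Can the combined rate be rebuilt from the printed rows?** With row rates a and b, max(a, b) ≤ combined rate ≤ min(1, a + b). The documents give no rates for fatigue or malaise, so these are assumptions:
- a = b = 5%: combined rate 5% to 10%, or 32 to 63 of 630.
- a = b = 10%: combined rate 10% to 20%, or 63 to 126 of 630.

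If only one label is ever recorded at a given time, the two TREF 3.11 rows at that time point do not overlap and their sum is the combined rate there. The any-day rows in TREF 3.12 can still overlap, because a participant may use one label on one day and the other on the next.

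**5. Effect on the comparison (illustration only).** Assume 30% of 630 against 20% of 315, labels chosen evenly and never both. For a two-sided 5% z-test, power = Φ[(|p1 − p2| − 1.96·SE0)/SE1], where SE0 uses the pooled proportion and SE1 the separate ones.
- Combined row: pooled proportion 252/945 = 0.267, SE0 = 0.0305, SE1 = 0.0290. Power = Φ[(0.10 − 0.0598)/0.0290] = Φ(1.39) ≈ 92%.
- Each split row, 15% v 10%: pooled proportion 126/945 = 0.133, SE0 = 0.0235, SE1 = 0.0221. Power = Φ[(0.05 − 0.0460)/0.0221] = Φ(0.18) ≈ 57%.
- At least one of the two split rows significant, by simulation: about 84%. With no true difference, at least one is significant about 10% of the time, against 5% for the single combined test.

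**The case against.** - **The protocol is not uniform.** Section 11.4 is the analysis section for safety, and its comma agrees with the SAP rows. This stands as a second inconsistency to repair. It does not justify the split, because the endpoint lists, the SAP's own synopsis and Appendix A all treat the pair as one.
- **The rate is recoverable.** Time-point sums work if one label is used at a time, and the systemic-reaction listing (SAP Appendix 05) holds subject-level entries. This stands. A reader might infer that the endpoint rate is lost, but the documents show only that no table shell plans it. FREF 07 and FREF 08 are figures whose content is not visible.
- **The harms depend on unseen recording practice.** The diary card and case report form are not in the documents. Understatement and double counting are alternatives, and neither is established.
- **The power argument is easily overstated.** A reader might infer from 92% against 57% that splitting hides a difference between the arms. The 30% and 20% rates are not in the documents, and two split tests together detect the difference about 84% of the time, at the cost of more false positives.
- **Swelling/induration is not the same problem.** A reader might infer that its rate is split and tested in halves as well. TREF 3.6 gives sizes only. The n in that table might supply a count for each term at each time point, but no percentage, grade or combined count is laid out. The gap is a missing rate.

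**Conclusion.** The point stands, within limits. For fatigue/malaise, the SAP tables do not report the reaction that the endpoint and Appendix A define. They report and test two parts, and TREF 3.14 has a maximum of nine where the definition gives eight. The combined any-day rate is known from the tables only to lie between the larger row and the sum of the two. For swelling/induration, no percentage or grade of the reaction is planned in any form. These conclusions come from the wording and the shells and need no assumed rates. The power figures do rest on assumed rates and are illustrative only.

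A reader might infer that the overall safety summary or the trial's main conclusion is compromised. The documents do not support that: the any-systemic maximum grade in TREF 3.10 is the same whether the pair is split or joined, and the immunogenicity conclusion does not use these data. The change is worth making because it aligns a primary safety output with its definition.

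**What to change.** - **TREF 3.11 to 3.13:** add one fatigue/malaise row, counted as present if either term is recorded and taken at the higher grade, with n (%), exact 95% CI and the between-arm comparison.
- **TREF 3.14:** count fatigue/malaise once, so the maximum is eight.
- **TREF 3.6 and 3.7:** add one swelling/induration row, counted as present if either term is recorded, using the larger diameter and graded by Appendix A, with n (%) and exact 95% CI.
- **TREF 3.9:** count swelling/induration once as a local reaction. It does not belong in TREF 3.14, which counts systemic reactions. State in the notes to TREF 3.5 and FREF 07 how the pair is handled, since they now name only induration.
- **Listings:** keep the separate terms in SAP Appendices 04 and 05.
- **Protocol section 11.4:** align the wording with the endpoint lists.

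The cost is a change to shells and programming, plus one wording correction. It assumes that the recorded data show whether either term was present, with its grade or diameter; the diary card and case report form should be checked for this. The separate labels remain available in the listings.

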# Secondary Immunogenicity Endpoints and analysis:

The secondary immunogenicity endpoints will be analyzed by the following:

- Number and percentage of participants with a HI antibody titer ≥1:40 (seroprotective level) to each of the three vaccine antigens measured on Day 21 and Day 90.
- Number and percentage of participants who develop at least a four-fold increase in HI antibody titers to each of the vaccine antigen post-vaccination measured on Day 21 and Day 90 segregated by pre-vaccination HI antibody titers (<1:10 or ≥1:10).
- Geometric mean fold rises (GMFRs) of serum HI antibodies (post-vaccination/pre-vaccination) for each of the three vaccine antigens.
- GMTs of serum HI antibodies pre- (Day 0) and post-vaccination (Day 21 and Day 90) for each of the three vaccine antigens segregated by pre-vaccination HI antibody titers (<1:10 or ≥1:10).
- GMFRs of serum HI antibodies (post-vaccination/pre-vaccination) for each of the three vaccine antigens segregated by pre-vaccination HI antibody titers (<1:10 or ≥1:10).

# Sample Size Calculation (1) :

The sample size calculation was planned for the ratio of 2:1. The SAS 9.4 statistical software, was used to calculate the sample size needed for the study under the assumption of a non-inferiority trial for binary outcome endpoint.

According to the recommendations for the co-primary endpoints, the sample size OVED

- The difference in seroconversion rate of active comparator vaccine and MITTEE Seroconversion rate of GPO Tri Fluvac should not exceed 10 percentage points.

- The difference in natural log of mean antibody titer between active comparator vaccine and GPO Tri Fluvac should not exceed 0.405, which is equivalence to the margin for GMT ratio = 1.5.

The sample size calculation was calculated using parameters of three strains of influenza under the study, including H1, H3, and Flu B. The parameter estimates for seroconversion and Standard deviation of natural log of antibody titer were obtained from previous study, phase II study of GPO Tri Fluvac.

Influenza strain	Titer Visit	Treatment Group	Sero- conversion	Mean of ln(titer)	
H1	Day 21	Vaccine	0.88	5.9728	
Н3	Day 21	Vaccine	0.535	5.36976	
Flu B	Day 21	Vaccine	0.865	4.75286	

The sample size calculation for non-inferiority test for proportions was performed with the margin of 0.1, assuming different seroconversion rate of the three influenza strain, and expected difference in seroconversion of the two groups is 0.000 with one-sided test alpha level 0.025 and power 0.8. Finally the sample size was adjusted for 7% not included in the ATP cohort. The required sample size for the study is as follow. The largest sample size required is 945 for total: 630 for study vaccine group and 315 for comparator vaccine group.

I wo group test of equivalence in proportions (large unequal n's)						
	H1	H3	Flu B			
Test significance level, α	0.025	0.025	0.025			
(one- sided)						
Standard proportion, $\pi_{S}$	0.880	0.535	0.865			
Equivalence limit difference,	0.100	0.100	0.100			
$\pi_{\rm T}$ - $\pi_{\rm S}$ , $\Delta_0$						
Test expected proportion, $\pi_T$	0.880	0.535	0.865			
Expected difference, $\pi_T - \pi_S$ , $\Delta_1$	0.000	0.000	0.000			
Power ( % )	80	80	81			
n S	125	293	134			
n T	250	586	276			
Ratio: n T / n S	2.000	2.000	2.000			
$N = n_S + n_T$	375	879	414			
Adjusted 7% not included in the AT	P cohort					
n S	134	315	148			
n T	268	630	296			
$N = n_S + n_T$	402	945	444			

The sample size calculation for noninferiority test comparing two mean was performed according to the standard deviation of natural log scale of antibody titer of the 3 influenza strains with the margin of 0.405 (equivalence to ln of GMT ratio at 1.5), assuming expected difference in mean of natural log scale of antibody titer between the two groups is 0.000 with one-sided test alpha level 0.025 and power 0.8. Finally the sample size was adjusted for 7% no included in the ATP cohort.

	The required sample size for the study is as follow. The largest sample size required is 354 for total: 236 for study vaccine group and 118 for comparator vaccine group.					
	Two group t-test of equivalence in means (unequal n's)					
		H1	H3	Flu B		
	Test significance level, $\alpha$ (one-sided)	0.025	0.025	0.025		
	Fauivalence limit difference A	0 405	0 405	0.405		
	Equivalence mint unter ence, $\Delta_0$	0.000	0.000	0.000		
	$\Lambda_{0} = \Lambda_{1}$	0.405	0.405	0.405		
	Common standard deviation, $\sigma$	1.082	1.119	1.233		
	Power (%)	80	80	80		
	n1	85	91	110		
	n2	170	182	220		
	Ratio: $n_2 / n_1$	2.000	2.000	2.000		
	$\mathbf{N} = \mathbf{n}_1 + \mathbf{n}_2$	255	273	330		
	Adjusted 7% not included in the ATL	P cohort 91	98	118		
	n T	182	195	236		
	$N = n_S + n_T$	273	293	354		
Study	cohort = 630:315 About 945 male and non-pregnant fem	ale adults, 18	8 to 49 year	rs of age.		
Population:						
Eligibility	Inclusion:				_	
Criteria:	- Age 18-49 years old on the day of screening, having Thai ID card or equivalent					
	- Able to read and write in Thai and	sign written	informed co	onsent form		
	- Able to attend all scheduled visits a	and to comply	y with all t	rial procedures	5.	
	- Healthy or medically stable, as e examination. For individuals wi present must be stable, under contr medication is used to treat the con- stable for at least one month preced	established b th medical rol or unchan ndition, the r ling vaccinat	by medical conditions nged for the medication ion.	history and j , symptoms/s e past three mo dose must ha	ohysical igns, if onths. If ve been	
	- For female participants:					
	• Not breast feeding, non-pregna and no plan to become pregnan	ant (based on it up to Day 6	n negative	urine pregnan	EV RSO	
	• Women who are not surgicall post-menopausal for more that	ly sterile (hy n one year 1	sterectomy must be wi	ot tubal liga	CSCON tion) or OF TROPIC effective	

	contraceptive method to prevent pregnancy until Day 60 after vaccination. Effective methods include intrauterine device, hormonal contraceptives (oral, injectable, patch, implant, ring) or double barrier contraceptives (condom or diaphragm with spermicide). Women with credible history of abstinence may be enrolled at the discretion of the investigator.	
	Exclusion:	
	- Participation in another clinical trial involving any therapy within the previous three months or planned enrollment in such a trial during the period of this study.	
	- Hypersensitivity after previous administration of any vaccine.	
	- Having a history of H1N1, H3N2 or FluB infection within 3 months preceding enrollment to the trial	
	- Vaccination against influenza in the past 6 months preceding enrollment to the trial	
	- Receipt of any non-study vaccine within four weeks prior to enrollment or refusal to postpone receipt of such vaccines until after the Day 21 visit.	
	- History of bronchial asthma, chronic lung diseases, chronic rhinitis	
	- History of immunodeficiency state	
	- History of immunosuppression < 6 months prior to immunization	
	- History of anaphylactic or other allergic reactions to influenza vaccine or any vaccine component or excipient (e.g. gentamicin or thimerosal)	
	- History of Guillain-Barré Syndrome.	
	
 
Having acute infection with fever > 38 degree Celsius or noninfectious diseases (within 72 hours) preceding enrollment in the trial
 
	
	- Volunteers who have been taking immunoglobulin products or have had a blood transfusion during past 3 months before the beginning of the trial or planned receipt of such products prior to the Day 21 visit.	
	- Current alcohol abuse or drug addiction that might interfere with the ability to comply with trial procedures	
	- Any condition that in the opinion of the investigator would pose a health risk to the subject if enrolled, or could interfere with the evaluation of the vaccine	
Phase:	II/III	
Study Duration	Approximately 1 year	
Participatio n Duration:	About three to four months per participant	
Description of Agent or Intervention	The vaccine is a seasonal trivalent inactivated split virion influenza vaccine recommended for Southern Hemisphere in 2017 (consisting of A/Michigan/45/2015 (H1N1)pdm-09-like virus, A/Hong Kong/4801/2014 (H3N2)-like virus, and PRO	VED
:	B/Brisbane/60/2008-like virus) produced by the Government Pharmaceutical Organization (GPO), Thailand. Each dose of Tri Kuvac contains ractotaloofr45	
	MANDOL UNI	/ LNOILY

	micrograms (µg) hemagglutinin (HA) per 0.5 ml dose (15 µg HA per strain per dose), to be administered by intramuscular (IM) injection. Tri Fluvac is manufactured and formulated into a multiple-dose vial vaccine (2 doses) using thimerosal at relatively low concentration as preservative ( $\leq$ 7.5 µg mercury/ dose). Each 0.5 ml dose of vaccine may contain residual amounts of ovalbumin ( $\leq$ 5.0 µg), formaldehyde ( $\leq$ 50 µg), tween 80 ( $\leq$ 250 µg), triton x-100 ( $\leq$ 5 µg) and gentamicin (not more than 0.05 µg). The vaccine should be administered as a single 0.5ml intramuscular injection, preferably in the region of the deltoid muscle of the upper arm.
Description of active comparator vaccine:	Licensed Influenza vaccine (seasonal trivalent inactivated split virion influenza vaccine recommended for Southern Hemisphere in 2017 (consisting of A/Michigan/45/2015 (H1N1)pdm-09-like virus, A/Hong Kong/4801/2014 (H3N2)-like virus, and B/Brisbane/60/2008-like virus) 0.5 mL administered intramuscularly (IM) in the deltoid muscle of the non-dominant arm.

APPROVED ETHICS COMMITTEE FACULTY OF TROPICAL MEDICINE MAHIDOL UNIVERSITY

